7.2.1 Demographics / baseline characteristics

Demographic and baseline characteristic data to be collected on all subjects include: age, sex, race, and ethnicity (if allowed in the country). Relevant medical history/current medical conditions (e.g., chronic and ongoing acute conditions, serious past conditions) present before signing the ICF will be recorded on the medical history CRF form. Where possible, diagnoses and not symptoms will be recorded.

Medical history of special interest will be captured on the specific Medical History CRF form and includes:

- Etiology of PAH.
- Date of initial diagnosis.
- Uptravi dose at screening.

For subjects who failed screening, at least the following data will be recorded in the CRF if available:

- Demographics.
- Inclusion criteria not met and exclusion criteria met.
- Medical history of special interest.
- Central laboratory and ECG results will be transferred to the sponsor if available.
- all AEs and SAEs.

7.2.2 Efficacy assessments

Not applicable.

7.2.3 Safety assessments

The definitions, reporting and follow-up of AEs, SAEs and pregnancies are described in Section 9.

7.2.3.1 *Physical examination*

Physical examination will be performed according to standard practice at site and guided by medical history and/or symptoms.

Information for all physical examinations must be included in the source documentation at the study site. The observations will be reported according to body system in the CRF as either normal or abnormal. Any abnormality must be specified on the corresponding CRF form, describing the signs related to the abnormality (e.g., systolic murmur) and not the diagnosis (e.g., mitral valve insufficiency). Clinically relevant findings (other than those related to PAH) that are present prior to signing the ICF must be recorded on the Medical History CRF form. Physical examination findings made after signing the ICF which meet the definition of an AE [see Section 9.1.1] must be recorded on the AE form of the CRF.

7.2.3.2 *Vital signs*

Pulse rate, SBP, and DBP will always be measured in a supine position and will be recorded in the CRF. It is recommended to assess vital signs on the same arm throughout the study and to allow the subject to rest for at least 5 minutes prior to each measurement.

During the i.v. selexipag treatment (Period 2), vital signs will be measured before start of the morning infusion of selexipag and 6 times after the start of infusion (time schedule of measurements is detailed in [Table 3](#)). On Day 3, vital signs will be measured on the arm where the line for PK sample collection is placed (opposite arm from infusion of selexipag) and vital signs are to be measured immediately prior to blood collection.

7.2.3.3 *Weight and height*

Body weight will be measured in indoor clothing but without shoes and recorded in the CRF.

Height will be measured without shoes and recorded in the CRF.

7.2.3.4 *ECG assessment*

Standard 12-lead ECGs will be recorded with the subject in a fully rested supine position. Prior to the measurement it is recommended to allow the subject to rest for at least 5 minutes.

A central ECG laboratory [see central ECG manual for contact details] will be used for all protocol-mandated ECGs [\[Table 2\]](#), including re-tests due to ECG abnormalities and ECGs performed at unscheduled visits.

Central ECG reports will be sent to the investigator. In the event of specific (pre-defined in the central ECG laboratory manual) ECG abnormalities, the central ECG laboratory will alert Actelion personnel and the concerned site personnel.

All ECG reports must be reviewed, signed, and dated by the investigator or delegate within 10 working days of receipt and filed with the source documentation. The investigator/delegate must indicate on the ECG report whether abnormal values or findings are considered clinically relevant or not.

Clinically relevant ECG findings that are known at the time of signing the ICF must be documented in the Medical History section of the CRF.

Clinically relevant ECG abnormalities detected after signing the ICF must be reported as an AE or SAE as appropriate.

The data records will be electronically transmitted to the central ECG laboratory for central reading. ECG data will be electronically transferred from the ECG laboratory database to Actelion. Details on ECG procedures (recording, transfer of data, and reporting) will be provided in the central ECG laboratory manual.

The following variables will be evaluated: HR (bpm), PR (ms), QRS (ms), QT (ms), QTcB (ms), QTcF (ms) and any ECG findings. QTc (ms) will be calculated according to Bazett's and Fridericia's formulae (i.e., QTcB = QT/ \sqrt{RR} and QTcF = QT/(RR) $^{1/3}$).

7.2.4 Laboratory assessments

7.2.4.1 Type of laboratory

A central laboratory [see central laboratory manual for contact detail]) will be used for all protocol-mandated laboratory tests, including re-tests due to laboratory abnormalities and laboratory tests performed at unscheduled visits.

Exceptional circumstances that will require recording of local laboratory results of the variables described in Section 7.2.4.2 (with corresponding normal ranges) include hospitalization of the subject due to a medical emergency and missing central laboratory results from a scheduled or unscheduled visit.

If a central laboratory sample is lost or cannot be analyzed for whatever reason, the investigator will consider collecting an additional sample as soon as possible if deemed medically needed for repeat analysis.

Central laboratory reports will be sent to the investigator. In the event of specific (pre-defined) laboratory abnormalities, the central laboratory will alert Actelion personnel and the concerned site personnel. Alert flags that will trigger such notifications are displayed in [Appendix 1](#).

All laboratory reports must be reviewed, signed, and dated by the investigator or delegate within 10 working days of receipt and filed with the source documentation. The investigator/delegate must indicate on the laboratory report whether abnormal values are considered clinically relevant or not. Clinically relevant laboratory findings that are known at the time of signing of informed consent must be recorded on the Medical History form of the CRF. Any study-emergent clinically relevant laboratory abnormalities detected after signing of informed consent must be reported as an AE or SAE as appropriate, and must be followed until the value returns to within the normal range or is stable, or until the change is no longer clinically relevant.

Details about the collection, sampling, storage, shipment procedures, and reporting of results and abnormal findings can be found in the laboratory manual.

7.2.4.2 Laboratory tests

Hematology

- Hemoglobin (g/L)
- Hematocrit (L/L)
- Erythrocytes ($10^{12}/L$)
- Leukocytes with differential counts ($10^9/L$)
- Platelets ($10^9/L$)

Clinical chemistry

- Alanine aminotransferase (U/L)
- Aspartate aminotransferase (U/L)
- Alkaline phosphatase (U/L)
- Total and direct bilirubin (μ mol/L)
- Creatinine (μ mol/L)
- Sodium, potassium (mmol/L)

Pregnancy test

Only for women of childbearing potential:

- Urine pregnancy test will be performed as standard assessment during this study.
- If pregnancy is suspected during the study, a serum pregnancy test must be performed immediately.

The results of the pregnancy tests will not be collected in the CRF.

7.2.5 Pharmacokinetic assessments

7.2.5.1 Pharmacokinetic assessments

PK blood samples will be collected for all subjects in order to establish a 12-hour PK profile at steady state for selexipag and ACT-333679 when subjects are at their stable dose of Uptravi and after the switch from Uptravi to i.v. selexipag.

7.2.5.1.1 Timing for sampling

For all subjects, a total of 14 blood samples will be drawn.

PK blood samples will be collected as displayed in [Table 3](#).

On Day 1, plasma concentrations of selexipag and ACT-333679 will be measured at pre-dose (trough) and 1, 2, 4, 6, 8, and 12 hours after the morning dose of Uptravi.

On Day 3, plasma concentrations of selexipag and ACT-333679 will be measured at pre-dose (trough) and 25 min, 87 min (i.e., immediately before stopping the infusion), 4, 6, 8, and 12 hours after initiation of the morning i.v. infusion of selexipag.

The allowed time window is \pm 5% from the scheduled time point (refer to laboratory manual for conversion table between % and minutes).

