5.1.4 Study treatment administration

The following infusion scheme is to be followed:

- Start with an infusion rate of 20 mL/h (0.333 mL/min) for 15 min for the first 5 mL.
- Increase infusion rate to 37.5 mL/h (0.625 mL/min) for 72 min for infusion of the remaining 45 mL.

Note: A dedicated infusion line must be used for i.v. selexipag administration. No other drugs or solutions should be administered through this line.

The following information will be collected in the CRF to document each i.v. selexipag administration:

- Date of administration.
- Concentration of the i.v. infusion solution.
- For each infusion rate: clock time of start and end.

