10.2.4 Pharmacokinetic variables

Plasma PK parameters of selexipag and its active metabolite, ACT-333679, will be derived by non-compartmental analysis of the concentration-time profiles. The PK parameters will be calculated on the basis of the real blood sampling time points (in relation to the last selexipag intake during each period).

The measured individual plasma concentrations of selexipag will be used to directly obtain $C_{trough, ss}$, $C_{max, ss}$, and $t_{max, ss}$.

$AUC_{\tau, ss}$ will be calculated according to the linear trapezoidal rule using the measured concentration-time values above the LOQ during one dosing interval at steady state.

For mean value calculations, all values below the limit of quantification (BLQ) will be set to zero. If > 50% of the values at a given time point are BLQ, no mean value will be calculated. Mean concentration-time profiles will be generated using these criteria.

$C_{max, ss}$, $C_{trough, ss}$, and $AUC_{\tau, ss}$, values are assumed to be log-normally distributed [Julious 2000].

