7.8.3 Pharmacokinetic variables

Plasma PK parameters of selexipag and its active metabolite, ACT-333679, will be derived by non-compartmental analysis of the concentration-time profiles.

The PK parameters will be calculated on the basis of the real blood sampling time points (in relation to the last selexipag intake during each period).

The measured individual plasma concentrations of selexipag will be used to directly obtain $C_{trough, ss}$, $C_{max, ss}$, and $t_{max, ss}$.

$AUC_{\tau, ss}$ will be calculated according to the linear trapezoidal rule using the measured concentration-time values above the limit of quantification (LOQ) during one dosing interval at steady state.

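### Day 3 has no PK sample between the end of infusion (87 min) and 4 h, so the linear trapezoid overstates i.v. selexipag AUC, while ACT-333679 AUC and Cmax are understated

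*Protocol*

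**What the plan says.** Protocol 7.2.5.1.1 sets the oral samples on Day 1 at "pre-dose (trough) and 1, 2, 4, 6, 8, and 12 hours after the morning dose of Uptravi". On Day 3 the i.v. samples are at pre-dose and then at "25 min, 87 min (i.e., immediately before stopping the infusion), 4, 6, 8, and 12 hours after initiation". The total is fixed: "For all subjects, a total of 14 blood samples will be drawn". Each sample has a window of plus or minus "5% from the scheduled time point".

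The AUC rule is the same in both documents. Protocol 10.2.4 says that AUC "will be calculated according to the linear trapezoidal rule using the measured concentration-time values above the LOQ during one dosing interval", and SAP 7.8.3 repeats it: "will be calculated according to the linear trapezoidal rule using the measured concentration-time values above" the LOQ. Neither has a log-down rule. The only optional PK sensitivity analysis (SAP 7.8.4.3) concerns implausible concentrations. Actual sampling times are used, which corrects for late or early draws but not for the gap.

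Blood pressure and pulse follow the same Day 3 time points (Protocol Table 3, SAP Table 9). A 12-lead ECG is scheduled within 30 minutes after each infusion ends (Protocol Table 2, footnote 7), so the interval is not free of all measurement.

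**The concern.** Selexipag concentration falls fastest just after the infusion stops. A straight line drawn across a convex decline lies above it, so the linear rule overstates area there. ACT-333679 is formed from selexipag and goes on being formed after the infusion ends. Its peak therefore comes later than 87 min and may fall where nothing is sampled. Its Cmax and tmax are then read at 1.45 h or 4 h, whereas the oral profile has a 2 h point.

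Three planned outputs are affected: the i.v./oral geometric mean ratios of AUC and Cmax for both analytes (key deliverables in SAP 12.8), the ACT-333679/selexipag ratios, and the ACT-333679 tmax shift. The primary objective presupposes matched exposure to ACT-333679, and SAP 3.1 names AUC and Cmax as examples of that exposure.

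**Working it through.** **Plan figures reproduced.** Samples: 7 + 7 = 14. Infusion (Protocol 5.1.4): "Start with an infusion rate of 20 mL/h (0.333 mL/min) for 15 min for the first 5 mL", then a second step "for 72 min for infusion of the remaining 45 mL". 5/20 h + 45/37.5 h = 15 + 72 = 87 min. Gap: 4 − 87/60 = 2.55 h. With the 5% windows it runs from 3.80 − 1.5225 = 2.28 h to 4.20 − 1.3775 = 2.82 h.

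**Error within the gap.** For an analyte falling exponentially with rate k = ln 2 / half-life over a gap d:

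error = [d/2 × (1 + e^(−kd))] / [(1 − e^(−kd))/k] − 1

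At a half-life of 1 h, e^(−kd) = 2^(−2.55) = 0.171. The linear area is 1.275 × 1.171 = 1.493 and the true area is 0.829/0.693 = 1.196, so the error is +25%. The same formula gives +87% at 0.5 h, +6.4% at 2 h and +1.6% at 4 h.

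**Error over the 12 h interval, selexipag.** The model has one compartment, the two-rate infusion twice daily to steady state, and the protocol's sampling times. The documents state neither half-life nor absorption rate. The assumed oral inputs are first-order absorption at 0.5 to 4 per h with a lag of 0 to 1 h. Ratio columns show the range over those inputs.

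| Parent half-life | i.v. AUC, linear | i.v. AUC, log-down | Oral AUC, linear | i.v./oral ratio, linear | i.v./oral ratio, log-down both |
|---|---|---|---|---|---|
| 0.5 h | +35% | −4.1% | −29% to +20% | +13% to +91% | −8% to +56% |
| 1 h | +14% | −1.6% | −14% to +12% | +1.5% to +32% | −6% to +23% |
| 1.5 h | +7.3% | −0.8% | −9% to +8% | −1.0% to +18% | −4% to +15% |
| 2 h | +4.6% | −0.4% | −7% to +6% | −1.5% to +12% | −3% to +11% |
| 4 h | +1.5% | −0.1% | −4% to +3% | −1.4% to +5% | −2% to +5% |

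At 2.5 h the linear i.v. error is about +3%.

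**ACT-333679 after i.v.** It is formed from parent in the same model. Selected cases (parent / metabolite half-life):

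| Half-lives | True tmax | Observed tmax | AUC error, linear | Cmax error |
|---|---|---|---|---|
| 0.5 / 2 h | 2.23 h | 1.45 h | −5.6% | −23% |
| 1 / 2 h | 2.81 h | 4.00 h | −4.6% | −11% |
| 1 / 6 h | 3.44 h | 4.00 h | −1.9% | −1.1% |
| 2 / 6 h | 4.39 h | 4.00 h | −1.2% | −0.3% |

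Over parent half-lives of 0.5 to 2.5 h and metabolite half-lives of 2 to 14 h:

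- Linear AUC error is −0.5% to −5.6%.
- With log-down it is −0.6% to −8.1%, which is worse.
- Cmax error is 0 to −23%.
- With a 2.5 h sample and the linear rule, AUC error is about −0.3% to +1% and Cmax is at most 4% low.

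The ACT-333679 i.v./oral AUC ratio error depends on the range assumed. It runs from about −9% to +2% for metabolite half-lives of 2 to 12 h and parent half-lives of 0.5 to 3 h. Allowing a 1 h metabolite half-life widens it to about −15% to +4%.

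**Metabolite/parent AUC ratio after i.v.** The two errors compound. At 0.5 / 2 h: 0.944/1.352 = 0.70, or 30% low. At 2 / 6 h: 0.988/1.046 = 0.94, or about 6% low.

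**The case against.** The strongest reply has four parts.

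- **The size cannot be known from the documents.** With no half-life given, 35% and 3% are both assumptions, and at a parent half-life of 2 h or more the error is 5% or less. This stands. Only the upward direction for i.v. selexipag AUC is independent of the value chosen.
- **The oral profile has its own grid error.** It uses the same linear rule with 2 h and 4 h intervals, and a fast early peak can be missed. This also stands. A reader might infer that every i.v./oral ratio is inflated. The calculations do not support that: the selexipag ratio error can reach −1% to −2% at half-lives of 1.5 h or more with slow absorption.
- **The exposure premise rests on ACT-333679, not selexipag.** Correct, and there the i.v. error runs downward. The large selexipag percentages therefore say nothing direct about the premise of the primary objective. Log-down for both analytes would also move the i.v. metabolite AUC further from the truth.
- **PK is descriptive.** It falls under the other objectives, with no hypothesis test or equivalence margin (Protocol 2.2 and 10.3.1, SAP 8.2). No stated decision turns on a few percent of AUC.

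The last part limits the consequence but does not remove the error. These are planned endpoints, and Protocol 1.3.1 says that the study is to support regulatory filings.

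**Conclusion.** The point holds in a limited form. The linear rule across the 2.55 h gap overstates i.v. selexipag AUC, by about 35% to 3% at assumed half-lives of 0.5 to 2.5 h. The selexipag i.v./oral ratio is biased upward throughout the inputs tried at half-lives of about 1 h or less. At longer half-lives it is usually biased upward. I.v. ACT-333679 AUC is understated by about 0.5% to 6% and Cmax by 0 to 23%. The Cmax loss is largest when both half-lives are short. Its tmax is read from a coarser post-infusion grid than the oral one.

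The sizes rest on a one-compartment model with assumed half-lives and absorption. A reader might go further and conclude that the exposure comparison is invalid or runs in one known direction. The documents do not support that, because the two analytes err in opposite directions and the oral profile contributes its own error. Nor is the interval unmonitored: an ECG is scheduled in it.

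**What to change.** 1. **AUC rule.** In Protocol 10.2.4 and SAP 7.8.3, calculate selexipag AUC by linear-up/log-down in both periods, or prespecify it as a sensitivity analysis. Keep the linear rule for ACT-333679. Record the change in SAP 11.1, which now lists none. This needs no new data. It brings the i.v. selexipag AUC error to between about −4% and 0%. It narrows the ratio error but does not remove it, because the oral grid error remains.
2. **If sampling is not complete,** add one Day 3 PK sample at about 2.5 h, with blood pressure and pulse taken first, as Protocol 7.2 already orders them. The cost is one draw and one cuff reading per subject in hospital (15 samples instead of 14), plus a protocol amendment. This is the only change that helps recover an ACT-333679 peak in the gap.
3. **If sampling is complete,** state in the SAP and the study report that i.v. ACT-333679 Cmax may be understated and tmax is only coarsely located. Say also that the tmax comparison is between two different grids. The cost is a few sentences.

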7.2.5.1.2 Procedures for sampling

Detailed instructions for the collection, preparation, labeling, storage, and shipment of the plasma samples can be found in the laboratory manual provided to the investigator.

Important points:

- Trough blood samples must be drawn before the morning dose of selexipag (oral or i.v.) is administered.
- 12-hour PK blood samples must be drawn before the evening dose of Uptravi is administered.
- PK blood samples on Day 3 must be taken from the opposite arm of infusion of i.v. selexipag, i.e., do not use the same arm for i.v. selexipag infusion and PK sampling.
- To prevent degradation of selexipag and ACT-333679 in the PK samples, exposure of the PK samples to light needs to be minimized.

The actual date and clock times of each PK blood sampling must be collected in the CRF.

7.2.5.1.3 *Bioanalysis*

The plasma concentrations of selexipag and ACT-333679 will be determined using a validated LC-MS/MS assay. The limit of quantification (LOQ) for both analytes in plasma is 0.01 ng/mL. Concentrations will be calculated by interpolation from a calibration curve. Quality control samples will be used to determine between-run and overall precision and accuracy of the analysis. No genetic analysis will be conducted.

7.2.5.1.4 *Shipping procedures*

The site staff will be responsible for the shipment of the plasma PK samples. Samples must be sent to the central laboratory ([REDACTED]), at time intervals as defined in the laboratory manual. The samples, together with the completed shipment forms, must be packed securely in polystyrene-insulated shipping containers containing enough dry ice to last for 48 h. The central laboratory will ensure subsequent shipment of the plasma PK samples to [REDACTED] Actelion.

8 STUDY COMPLETION AND POST-STUDY TREATMENT / MEDICAL CARE

8.1 Study completion

A subject who received at least one dose of i.v. treatment and performed the follow-up period is considered to have completed the study.

8.2 Premature withdrawal from study

Subjects may voluntarily withdraw from the study without justification for any reason at any time. Subjects are considered withdrawn if they state an intention to withdraw further participation in all components of the study (i.e., withdrawal of consent), die, or are lost to follow-up. If a subject withdraws consent, no further data will be collected in the CRF

from the date of withdrawal onward. The investigator may withdraw a subject from the study (without regard to the subject's consent) if, on balance, he/she believes that continued participation in the study would be contrary to the best interests of the subject. Withdrawal from the study may also result from a decision by Actelion for any reason, including premature termination or suspension of the study.

Subjects are considered as lost to follow-up if all reasonable attempts by the investigator to communicate with the individual failed. The site must take preventive measures to avoid a subject being lost to follow-up (e.g., document different ways of contact such as telephone number, home address, email address, person to be contacted in case the subject cannot be reached). If the subject cannot be reached, the site must make a reasonable effort to contact the subject, document all attempts, and enter the loss of follow-up information into the CRF. The following methods must be used: at least three telephone calls must be placed to the last available telephone number and one registered letter must be sent by post to the last available home address. Additional methods may be acceptable if they are compliant with local rules/regulations (e.g., a visit by site personnel to the subject's home), respecting the subject's right to privacy. If the subject is still unreachable after all contact attempts listed above, he/she will be considered to be lost to follow-up.

If premature withdrawal occurs for any reason, the reason (if known) for premature withdrawal from the study, along with who made the decision (subject, investigator, or Actelion personnel) must be recorded in the CRF, if known.

If, for whatever reason (except death or loss-to-follow-up), a subject is withdrawn from the study, the investigator should make efforts to schedule a last appointment / telephone call to assess the safety and well-being of the subject, collect unused study treatment and discuss follow-up medical care. Data obtained during this last appointment / telephone call will be recorded in the subjects' medical records but it will not be collected in the CRF. The investigator must provide follow-up medical care for all subjects who are prematurely withdrawn from the study, or must refer them for appropriate ongoing care, as described in Section 8.4.

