9.1.4 Reporting of adverse events

All AEs with an onset date after signing of informed consent and up to 30 days after study treatment discontinuation (i.e., EOS visit / telephone call) must be recorded on specific AE form of the CRF.

Reporting of AE in CRF will include onset time.

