9.2.2 Reporting of serious adverse events

All SAEs occurring after signing of informed consent up to 30 days after study treatment discontinuation must be reported on AE forms in the CRF and on an SAE form, regardless of the investigator-attributed causal relationship with study treatment (i.v. selexipag) or study-mandated procedures.

An SAE is defined as related to protocol-mandated procedures if it appears to have a reasonable possibility of a causal relationship to either the study design or to protocol-mandated procedures.

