5.1.3 Study completion/discontinuation

Subjects who received at least one dose of i.v. selexipag and who have completed the follow-up period will be considered study completers.

Subjects may discontinue from the study by withdrawal of consent, loss to follow-up, death, or investigator or sponsor decision. Details of study discontinuation are collected in the electronic case report form (eCRF).

The number and percentages of subjects who completed or prematurely discontinued the study, and reasons for discontinuation from the study will be summarized in a table and in a listing.

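### Protocol 8.2 bars last-contact safety data from the CRF even when consent stands, contradicting the 30-day AE and SAE recording rules in 9.1.4 and 9.2.2

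*Protocol*

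**What the plan says.** Protocol Section 8.2 has two separate rules on data after withdrawal.

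- **Consent withdrawn.** "If a subject withdraws consent, no further data will be collected in the CRF" from that date on.
- **Last safety contact.** The later paragraph opens "If, for whatever reason (except death or loss-to-follow-up), a subject is withdrawn from the study" and asks the investigator to try to arrange a final appointment or call to check the subject's safety. The data from it "will be recorded in the subjects' medical records but it will not be collected in the CRF".

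The same section allows withdrawal by people other than the subject. On best-interest grounds, "The investigator may withdraw a subject from the study (without regard to the subject's consent"). On the sponsor's side, "Withdrawal from the study may also result from a decision by Actelion for any reason", and early termination or suspension of the study is named as one such reason. SAP 5.1.3 lists the same routes: "Subjects may discontinue from the study by withdrawal of consent, loss to follow-up, death, or investigator or sponsor decision".

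The AE rules are in Section 9. Under 9.1.4, AEs starting between consent and 30 days after study treatment discontinuation "must be recorded on specific AE form of the CRF". Under 9.2.2, SAEs in that window "must be reported on AE forms in the CRF and on an SAE form". Table 2 footnote 10 repeats the 30-day window. None of the three exempts withdrawn subjects.

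**The concern.** Stopping CRF entry when a subject revokes consent is proper, and 8.2 already says so in its own sentence. The second rule is wider than that reason supports. It reaches subjects whose consent still permits collection, and it applies to a contact whose stated purpose is to assess safety.

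This matters because the analysis sees only the CRF. Protocol 10.2.3.1 defines an AE as an event recorded on the AE CRF module, and SAP 7.2.2 uses the CRF start date and time to place each AE in a period. Under protocol 6.2.2 the main safety endpoints run over Periods 1 to 3 and follow-up combined, so late AEs count. The study has no efficacy endpoint; safety and tolerability are its primary objective. Withdrawal on best-interest grounds is plausibly related to how the subject is doing, so any under-recording would tend to lower AE rates.

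**Working it through.** **1. Which subjects are caught in the conflict?**

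| Route out of the study | Does the 8.2 last-contact rule apply? | Do 9.1.4 and 9.2.2 still ask for CRF entry? | Result |
|---|---|---|---|
| Death or loss to follow-up | No, excepted | Yes, for what is known | No conflict |
| Consent withdrawn | Yes | Not after the withdrawal date, by the separate consent rule in 8.2 | Properly closed |
| Investigator decision, consent stands | Yes | Yes, to 30 days | Conflict |
| Sponsor decision, consent stands | Yes | Yes, to 30 days | Conflict |

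Suppose a subject in one of the last two rows first reports, at the last contact, an AE that began within the 30 days. Section 8.2 sends it to the medical record only; 9.1.4 sends it to the CRF AE form. A site cannot do both.

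**2. When in the study does this bite?** Protocol 5.1.10 defines premature discontinuation of study treatment as the third infusion not having been started. For those subjects, 5.1.10 and 7.1 recommend the Visit 3 assessments and make the Visit 4 call mandatory while consent for it stands. A subject withdrawn by the investigator during Period 2 can fall under both 5.1.10 and 8.2, which then disagree. Once the third infusion has started, 5.1.10 no longer applies and 8.2 is the only text on withdrawal. The exposure is therefore mainly in Period 3 and follow-up. Section 3.1.2 does not help: it gives alternatives to the Visit 4 call as End-of-Study only for consent withdrawal and loss to follow-up.

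**3. What is still captured?**
- AEs known before the last contact, including one that prompted the withdrawal (9.1.4).
- The reason for withdrawal and who decided, in the CRF (8.2).
- SAEs, on the SAE form to the sponsor within 24 hours (9.2.5). Only their CRF entry is in doubt.

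What remains exposed is non-serious AEs first reported at the last contact, plus CRF entry of SAEs learned there.

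**4. Size.** The interval is the two-sided 95% Clopper-Pearson interval (protocol 10.3.4). With x cases in n, the upper bound is the 0.975 quantile of Beta(x + 1, n − x).

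- Plan's own figures (protocol 10.5), which reproduce with two events: 2/18 gives an upper bound of 34.7%, below the stated 35%; 2/20 gives 31.7%, below the stated 32%.
- One case recorded in 18: 1/18 = 5.6%, upper bound 27.3%.
- That case lost: 0/18 = 0%, upper bound 1 − 0.025^(1/18) = 18.5%.
- Change: 5.6 points in the estimate and 27.3 − 18.5 = 8.8 points in the upper bound.
- Starting from two cases instead: 2/18 (11.1%, upper bound 34.7%) becomes 1/18 (5.6%, upper bound 27.3%).

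This shows the sensitivity to one unrecorded case. It is not a forecast, because the documents give no expected number of investigator or sponsor withdrawals.

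**The case against.** The strongest reply is that this is a wording slip with little reach. Much of it stands.

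- A reader might infer that 8.2 discards AEs generally in subjects stopped for safety. The documents do not support that. Those stopped before the third infusion have the mandatory Visit 4 call while consent stands, and the event behind a withdrawal is normally known before the last contact.
- A reader might infer that every withdrawn subject is affected. Death and loss to follow-up are excepted, and for consent withdrawal the exclusion is correct.
- A reader might infer that the endpoint of discontinuation due to prostacyclin-associated AEs is biased. It depends on the action-taken field for i.v. selexipag (SAP 7.2.1.4) and SAP Table 7 shows it for Period 2, the 36-hour in-hospital phase. It is largely unaffected.
- A reader might take 1 or 2 of 20 as the expected number, from the 10% in protocol 10.5. That figure concerns early discontinuations and is explained there as about 18 subjects entering the i.v. period (20 × 0.90 = 18). It is not a rate of investigator or sponsor withdrawal. On that reading the missing subjects never receive i.v. drug, so they lie outside the set of 18 and have no i.v. stop date from which to count 30 days.
- A reader might infer that 30 days of follow-up per subject are lost. The rule concerns the data from one contact.

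The reply does not remove the contradiction. For a consenting subject withdrawn by the investigator or sponsor, the instructions remain incompatible. If the sponsor ended the study early, 8.2 read literally would apply to each ongoing subject withdrawn as a result.

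**Conclusion.** The contradiction is real and should be corrected, but its effect is limited. It concerns subjects withdrawn by the investigator or sponsor with consent intact, chiefly after the third infusion has started. The loss is mainly non-serious AEs first reported at the last contact, plus CRF entry of SAEs. Any resulting error is an under-count of AE incidences that run through follow-up.

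The shift from 1/18 to 0/18 rests on three assumptions: the AE is first disclosed at that contact, it is that subject's only qualifying event, and no other subject in the set has one. The number of subjects at risk is unknown and may be zero. The case for the change is that the rules should agree and that the correction is cheap; it does not depend on an expected large bias.

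**What to change.** In protocol 8.2:

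1. Limit the sentence that keeps last-contact data out of the CRF to subjects who have withdrawn consent.
2. Add that, for all other withdrawn subjects, AEs and SAEs with onset up to 30 days after the last i.v. infusion, including those learned at the last contact, are entered in the CRF under 9.1.4 and 9.2.2.

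An early last contact should not be relabelled as the End-of-Study call. That call is set at 30 to 37 days after the last i.v. dose, so relabelling would close AE follow-up before the 30-day window has run. Where consent stands, the Visit 4 call should stay at its planned time.

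The cost is this change to 8.2, a matching CRF completion note, a little data entry and, for a few subjects, keeping a telephone call that is already in the schedule. The last contact is already requested by 8.2.
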